STUDY PROTOCOL WITH STATISTICAL ANALYSIS PLAN

Official title:

A Cost-efficiency Analysis of Primary Assessors for Patients With Knee Pain in Primary Care

NCT number: NCT03822533

The Regional Ethical Review Board in Gothenburg approved the study 2013-03-15, reference numbers: 979–12, T674–13, T497–14, T791–15 and 2020-00432.

Document date: Protocol published and released on clinicaltrial.gov 2019-01-30. Minor spelling and grammar changes made 2022-08-08, which are highlighted in yellow.

Sponsors: Region Vastra Gotaland, Närhälsan, Sweden

Principal Investigator: [name]

Närhälsan Research and development center Södra Älvborg

Contact person: [name]-student

Närhälsan Lidköping Rehabilitation center

Study Description

Brief Summary

Background: Almost half of the Swedish population are overweight or obese. This will probably affect the incidence of osteoarthritis since overweight is a strong risk factor. Osteoarthritis consultations is expected to increase with 30-50% within the next 20 years. Today, in Swedish primary care, both physicians and physiotherapists are primary assessors for patients with suspected knee osteoarthritis. A task shifting with physiotherapists as the only primary assessor could increase the access rate to physicians in primary care for patients with more severe disorders. Yet, it is unclear what effects these different healthcare processes have and the costs of it.

Purpose: The overall purpose of this study is to perform an economic evaluation of two healthcare processes, where a healthcare process initiated by a physiotherapist is compared with when it is initiated with a physician for patients with suspected knee osteoarthritis.

Methods: 100 patients will be randomized either to a physiotherapist or to a physician for first assessment, diagnosis and treatment. Measurements of health-related quality of life and costs for visits to physiotherapist, physician or other healthcare provider, drug prescriptions and sick-leave will be collected. A cost-effectiveness analysis will be conducted, presenting incremental cost-effectiveness ratio (ICER) and a non-parametric bootstrapping will be conducted to demonstrate the uncertainties surrounding the ICER.

Expected results: It is expected that this randomized controlled study will show the effects on quality adjusted life years, cost-efficiency, and cost-utility of two different primary assessors for patients with suspected knee osteoarthritis consulting primary care. The results could clarify which profession that is most appropriate to be the primary assessor for patients with suspected knee osteoarthritis in primary care.

.....

Detailed Description

Problem statements

What is the difference in cost efficiency between a healthcare process with a physiotherapist as primary assessor and a physician as primary assessor for patients with suspected KOA?

Which effect does a clinical pathway with a physiotherapist as primary assessor for patients with suspected knee osteoarthritis have on quality adjusted life years compared with a physician as primary assessor?

What are the differences in costs between the two healthcare processes initiated by either a physiotherapist or a physician set against the differences in effects?

Patient recruitment

Some data has already been collected for another clinical trial (ID: NCT03715764), which will be used in this study too. The patient recruitment is finished, while data collection regarding cost variables has not started yet.

Patients were recruited from primary care centers and rehabilitation centers in southwestern Sweden.

Screening procedure

Nurses and administration personnel at the recruitment units got information about the study and the screening protocol from the data collector and project leader. Each recruiting unit had a contact person that were responsible for the protocols and to contact the data collector when an eligible patient was found. It was regular contact between the project leader and the contact persons at the recruiting units. All screening protocols were sent to the data collector. All participants got orally and written information about the study from the data collector, and patients provided written informed consent.

Randomization

A computer-generated list of random numbers was used, where participants were randomly assigned to being assessed, diagnosed and treated either by a physiotherapist or a physician first. The project coordinator managed the sequence generation, allocation concealment, enrolment and assignments of participants and kept the concealed randomization scheme and sequentially numbered, sealed envelopes in a locked cupboard (in the same building where the enrolment was), only available for the project coordinator. The project coordinator revealed the allocation to the participant shortly after the baseline measurement and to the health care providers. Data collector, data analyst and statistician were blinded of allocation until completion of data collection for the primary outcome measures at the 12 months follow up for the last recruited patient. Group allocation was revealed when analyzing data for the other clinical trial (ID: NCT03715764).

The project coordinator was not involved in the screening procedure nor the data collection and was **not** included among the healthcare providers in the study. The blinded data collector and analyst, whom is a physiotherapist, were not involved in assessing, diagnosing and treating patients with knee osteoarthritis while the first study (ID: NCT03715764) was conducted.

Data collection

Demographic data and measurements of **health-related quality of life** (HrQoL) has already been collected for another clinical trial (ID: NCT03715764). These data will also be used for the cost-efficiency analysis. Demographic data were collected at baseline. Measurements of HrQoL were measured with EuroQol 5 dimensions 3 levels (EQ5D-3L) and collected at baseline (before randomization), 3-, 6- and 12 months follow ups.

New data collection will be made for cost variables. Data regarding costs for the healthcare processes will be extracted from patient journals. The costs for visits to **physiotherapist**, physician or other healthcare provider will be collected from the healthcare organization. The drug prices will be collected from the Swedish Association of Local Authorities and Regions for the time period the drugs were prescribed. Production loss due to sick-leave and health care visits will be valued according to mean gross salary (including taxes and social fees).

Calculating total costs (number of contacts per patient * costs) for:

- Physiotherapy contacts in primary care
- Physician contacts in primary care
- Referrals to x-ray
- Referrals to other healthcare givers
- Drug prescriptions
- Sick-leave days

Data management

All data will be coded and managed according to the General Data Protection Regulation. All data will be confidential and only authorized will have access to the patient registry. No individual information can be identified since the results will be presented at group level. Data will be saved for at least 10 years to enable audit.

Sample size

A sample size of 50 patients per group will be necessary to detect a minimal clinical improvement of 0.121(SD 0.2) on the EQ5D-3L-index, given an anticipated dropout rate of 14%. The sample size calculation was calculated with a two-sided 5% significance level and a power of 80%.

Statistical analysis plan

Data will be analyzed descriptively and presented as numbers and percent, mean and standard deviation or median and 25th to 75th percentiles. Statistical analysis will be made in SPSS Windows and the analysis will be applied with intention-to-treat (ITT).

The economic evaluation will be developed together with a health economist. The method will be a cost-effectiveness analysis alongside the clinical trial comparing costs and effects for the two alternatives based on collected data from the trial. The EQ5D-3L measurements will be used for analyzing quality adjusted life years. The result will be presented as an incremental cost-effectiveness ratio (ICER) and a non-parametric bootstrapping will be conducted to demonstrate the uncertainties surrounding the ICER.

Study Design

Study Type: Interventional (Clinical Trial)

Actual Enrollment: 69 participants

Allocation: Randomized

Intervention Model: Parallel Assignment

Participants with suspected knee osteoarthritis **were** either randomized to a physiotherapist or a physician as primary assessor for assessment and treatment. After the first assessment that the patients **were** assigned to, the patients **could** choose to seek the other health care provider if they **wanted** to. This study focuses on analyzing cost efficiency of the health care processes for patients with suspected knee osteoarthritis in primary care.

Masking: Single (Outcomes Assessor)

Primary Purpose: Treatment

Arms and Interventions

Physiotherapist as primary assessor - Intervention

The healthcare process will be started with a physiotherapist assessment and treatment. Treatments could involve individual or group treatment including patient education and physical exercise. Patients can seek a physician anytime after the first assessment with the physiotherapist.

Physician as primary assessor – control

The healthcare process will be started with a physician assessment and treatment. Treatments could involve drug prescription, referral to x-ray, referral to other healthcare providers and sick-leave.

Patients can seek a physiotherapist anytime after the first assessment with the physician.

Outcome Measures

Primary Outcome Measures

Health related quality of life

[Time Frame: Baseline to one year after baseline.]

A Swedish version of Euroqol-5 dimensions-3 levels (EQ5D-3L) was used to assess perceived self-rated HrQoL. EQ5D-index respectively EQ5D-VAS will be presented. The questionnaire contained five dimensions and resulted in an index ranging from -0,549 to 1 using the UK tariffs. An index of 1 indicate full health. The EQ5D-VAS is a visual analogue scale ranging from 0 to 100, where 0 is worst imaginable health state and 100 is best imaginable health state.

Secondary Outcome Measures

A) Costs for physiotherapy contacts

[Time Frame: Baseline to one year after baseline.]

Number of visits registered in patients journal * cost

B) Costs for physician contacts

[Time Frame: Baseline to one year after baseline.]

Number of visits registered in patients journal * cost

C) Costs for sick-leave

[Time Frame: Baseline to one year after baseline.]

Number of sick-leave periods, including number of days with sick leave * costs

D) Costs for drug prescription

[Time Frame: Baseline to one year after baseline.]

Number of drug prescriptions* costs

E) Costs for referral to x-ray

[Time Frame: Baseline to one year after baseline.]

Number of referrals to an x-ray examination of the knee * costs

F) Costs for referral to other healthcare professionals

[Time Frame: Baseline to one year after baseline.]

Number of referrals to other professionals for an examination of the knee * costs

Eligibility Criteria

Ages Eligible for Study: 38 Years and older (Adult, Older Adult)

Sexes Eligible for Study: All

Accepts Healthy Volunteers: No

Inclusion Criteria

- Knee pain most of the days the last month
- Over 38 years old
- Crepitus on active motion
- Morning stiffness less than 30 minutes

Exclusion Criteria

- Not been diagnosed for current knee pain
- Non-traumatic cause due to current knee pain
- No other rheumatic, severe somatic or psychological diseases that can affect the outcome measures.
- Not pregnant
- Does not know enough Swedish to answer questionnaires.

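### The stated 80% power belongs to 100 patients, but recruitment closed at 69 and the plan never restates what 69 can detect (about 63% to 70% power on its own assumptions)

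*Combined protocol and SAP*

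**What the plan says.** Four places in the combined protocol and SAP give the size of the study or its recruitment status.

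- Brief Summary, Methods: "100 patients will be randomized either to a physiotherapist or to a physician for first assessment, diagnosis and treatment".
- Patient recruitment: "The patient recruitment is finished, while data collection regarding cost variables has not started yet".
- Sample size: "A sample size of 50 patients per group will be necessary to detect a minimal clinical improvement of 0.121(SD 0.2) on the EQ5D-3L-index", with an anticipated dropout of 14%. It adds: "The sample size calculation was calculated with a two-sided 5% significance level and a power of 80"%.
- Study Design: "Actual Enrollment: 69 participants".

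The EQ5D-3L is the primary outcome measure. For its two scores, the outcome section says "EQ5D-index respectively EQ5D-VAS will be presented". Under Data collection, the quality-of-life data are described as data that "has already been collected for another clinical trial (ID: NCT03715764). These data will also be used for the cost-efficiency analysis". Under Randomization: "Group allocation was revealed when analyzing data for the other clinical trial (ID: NCT03715764").

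**The concern.** A planned number and an achieved number can stand in one document, provided that each is labelled and the gap is acknowledged. Here neither is done. The summary speaks of 100 patients in the future tense although recruitment has closed with 69. No section says that the target was missed by 31 patients (100 − 69), gives the number in each arm, or restates the sensitivity of the study. The only such statement for the index therefore describes a sample that was not reached.

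The practical risk lies in how a non-significant index result is read. The analysis section names no test, but a sample size based on a two-sided 5% level implies a between-group comparison. A reader who takes the 80% at face value would give a null result more weight than 69 patients can support.

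**Working it through.** **Inputs from the document.** Difference 0.121, SD 0.2, two-sided 5%, power 80%, dropout 14%, 50 per group (all Sample size); 69 enrolled (Study Design).

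**Assumed, because the document does not say.** A near-equal split between arms, either 14% or no dropout among the 69, and an unadjusted two-sample t-test.

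**1. The plan's own figure.** With the normal formula,

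n per group = 2 × (1.960 + 0.842)² × (0.2/0.121)² = 42.9, rounded up to 43 evaluable.

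43 / (1 − 0.14) = 50 per group. The stated figure reproduces exactly. Power at 43 per group is 0.80 by the normal formula and 0.79 by the noncentral t, which is the basis used below.

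**2. Evaluable patients from 69.** With no dropout, 69 (34/35). With 14% dropout, 69 × 0.86 = 59.3, about 59 (29/30). The plan needs 2 × 43 = 86 evaluable, so no retention rate at 69 reaches it.

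**3. Power and precision at SD 0.2.** The standard error is 0.2 × √(1/n₁ + 1/n₂). Power comes from the noncentral t with noncentrality 0.121/SE. The 95% CI half-width is t(0.975; n₁ + n₂ − 2) × SE.

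| Evaluable | SE | Power for 0.121 | Detectable at 80% power | CI half-width |
|---|---|---|---|---|
| 43/43 (plan) | 0.0431 | 0.79 | 0.122 | 0.086 |
| 34/35 (no dropout) | 0.0482 | 0.70 | 0.137 | 0.096 |
| 29/30 (14% dropout) | 0.0521 | 0.63 | 0.148 | 0.104 |

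Unrounded, the half-widths are 0.0858, 0.0961 and 0.1043. The intervals are thus 12% wider (0.0961/0.0858) and 22% wider (0.1043/0.0858) than planned.

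**4. What this does to a null result.** If the true difference is 0.121, the chance of a non-significant result is 1 − power: 0.21 as planned, 0.30 with all 69 evaluable, 0.37 with 14% dropout. An observed difference is non-significant yet still compatible with 0.121 when it lies between 0.121 − half-width and the half-width:

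- plan: 0.035 to 0.086
- no dropout: 0.025 to 0.096
- 14% dropout: 0.017 to 0.104

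This zone existed at the planned size; the shortfall widens it.

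**5. Sensitivity of the power for 0.121.**

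| Assumption | 43/43 (plan) | No dropout | 14% dropout |
|---|---|---|---|
| SD 0.18 | 0.87 | 0.79 | 0.72 |
| SD 0.20 | 0.79 | 0.70 | 0.63 |
| SD 0.25 | 0.60 | 0.51 | 0.45 |
| SD 0.20, uneven split (28/41 or 24/35) | – | 0.68 | 0.61 |

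The unknown split matters little. The SD matters more, but it moves the planned design as well, so the effect of the shortfall is the difference along each row.

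**The case against.** The best reply is that the document hides nothing. The 69 is printed shortly after the Sample size paragraph, and that paragraph is in planning language: it does not claim 80% power for 69 patients. The analysis section centres on QALYs, the ICER and a bootstrap. It names no test of the index, and nothing in the plan proposes to read non-significance as equal effect. This stands in part. It limits the point to the index and makes the misreading a risk rather than a planned step. It does not supply the missing link between the two numbers, and the future-tense 100 is plainly out of date.

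A second reply is that power could be higher with a baseline-adjusted analysis. If SD 0.2 is the spread at a single visit and the baseline correlation is 0.5 (neither is in the document), power would be about 0.75 with 14% dropout and 0.82 with none. At correlation 0.3 it would be 0.67 and 0.74. That is true, but no adjustment is planned, and it would raise the power of the planned 100 as well. It is a reason to call the 63% and 70% conditional.

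A third reply is that a detectable difference cannot alter a design whose data already exist, and that the confidence interval then carries the precision. That is fair, and the interval is the more important item. However, the usual criticism of post-hoc power concerns power computed from the observed effect. Here 0.121 and 0.2 stay fixed and only the number of patients is updated.

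Finally, the document calls 0.121 a minimal improvement without saying whether that is a within-patient or a between-group threshold. Since 0.121 reproduces 50 per group as a two-group difference, reading a between-group interval against it is consistent with the plan's own use.

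**Conclusion.** The point holds and should be fixed. The calculation is right for 100 patients, but the stated size and power were not delivered and the document does not say so. On the same t-test basis the loss is about 16 percentage points with 14% dropout (0.79 to 0.63) or 9 with none (0.79 to 0.70). These figures rest on SD 0.2, a near-equal split and an unadjusted analysis; they are placeholders until the actual numbers per arm are stated. That power falls short of plan at SD 0.2 does not depend on the dropout rate, since 69 is below the 86 evaluable patients required. The conclusion does not extend to QALYs or to the uncertainty around the ICER.

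**What to change.** 1. In Sample size, label the existing calculation as the original plan and add: *Recruitment closed at 69 of the planned 100 ([n] physiotherapist first, [n] physician first); [n] and [n] have EQ5D-3L index data at 12 months. With these numbers and SD 0.2, a two-sided 5% t-test has 80% power for a difference of [x].* Compute [x] from the actual counts; expect about 0.148 if 14% are missing and 0.137 if none are.
2. In the Brief Summary, replace the future-tense 100 with planned 100, enrolled 69.
3. Report the between-group difference in the index with its 95% CI and read it against 0.121.

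The cost is wording plus counts that the sponsor should already hold, given that the index data were collected and allocation was revealed for the other trial. The stated sensitivity becomes less favourable. No extra patients, new data collection or change to the ICER analysis is needed.

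### The SAP names no adjustment of the incremental QALY for baseline EQ-5D-3L; adding it would make the ICER denominator more precise using data already held

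*Combined protocol and SAP*

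**What the plan says.** The Problem statements ask what effect a physiotherapist-first pathway would "have on quality adjusted life years compared with a physician as primary assessor". The Statistical analysis plan answers this within an economic evaluation "comparing costs and effects for the two alternatives based on collected data from the trial". It adds that "The EQ5D-3L measurements will be used for analyzing quality adjusted life years" and that "a non-parametric bootstrapping will be conducted to demonstrate the uncertainties surrounding the ICER". It mentions ITT and descriptive summaries, and leaves the development of the economic evaluation to work with a health economist. Neither this section nor any other names a regression model or covariate for the QALY difference.

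Other elements are fixed. Data collection states that EQ-5D-3L was "collected at baseline (before randomization), 3-, 6- and 12 months follow ups". Primary Outcome Measures states that the questionnaire "resulted in an index ranging from -0,549 to 1 using the UK tariffs", over one year.

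Under Randomization, "A computer-generated list of random numbers was used"; no stratification or other balancing on EQ-5D is described. The same section says: "Group allocation was revealed when analyzing data for the other clinical trial". Study Design gives an actual enrolment of 69.

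**The concern.** The incremental QALY is the denominator of the ICER and the direct answer to one of the study's own questions. A patient's QALY over the year usually depends on where that patient started, and the baseline index is itself one of the points on the QALY curve. With no balancing on EQ-5D, the arms can differ at baseline by chance, and a plain difference in mean QALYs carries that variation with it. Regression on the baseline index removes it.

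What is at stake is precision. Recruitment is finished, so precision cannot come from more patients, but the baseline index is already in the data set. A second, smaller issue is timing: while the estimator is open, it can be chosen after allocation and EQ-5D results are known from the companion trial.

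**Working it through.** **The plan's own figure.** Sample size gives a difference of 0.121, SD 0.2, two-sided 5%, power 80% and dropout 14%. Then n = 2 × [0.2 × (1.960 + 0.842) / 0.121]² = 42.9, rounded up to 43 per arm, and 43 / 0.86 = 50. The stated 50 per group reproduces, so SD 0.2 is the input that was used.

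**Inputs for the check.** From the documents: SD 0.2, visits at 0, 3, 6 and 12 months, 69 patients. Assumed, because the documents do not give them: SD 0.2 at every visit, trapezoid QALYs, a 34/35 split, complete data, and one correlation r between all pairs of visits.

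**Weights.** The trapezoid rule gives 0.125, 0.25, 0.375 and 0.25 at the four visits. Their squares sum to 0.28125.

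**Formulas.**
- Var(QALY) / SD² = 0.28125 + 0.71875r
- Cov(QALY, baseline) / SD² = 0.125 + 0.875r
- R² = Cov² / Var, both in units of SD²
- Unadjusted SE = 0.2 × √[Var × (1/34 + 1/35)]
- Adjusted SE = unadjusted SE × √(1 − R²)

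| r | Var/SD² | Cov/SD² | R² | SE unadjusted | SE adjusted | Reduction |
|---|---|---|---|---|---|---|
| 0.3 | 0.4969 | 0.3875 | 0.302 | 0.0339 | 0.0284 | 16% |
| 0.5 | 0.6406 | 0.5625 | 0.494 | 0.0385 | 0.0274 | 29% |
| 0.7 | 0.7844 | 0.7375 | 0.693 | 0.0427 | 0.0236 | 45% |

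**Cost of estimating the slope.** This multiplies the adjusted SE by √(1 + 1/65) = 1.008. The reductions become 15.8%, 28.3% and 44.2%. Simulated trials of 34 versus 35 patients (6,000 per r) gave 15.4%, 27.9% and 43.5%.

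**The same effect seen as imbalance.** The SE of the baseline difference is 0.2 × √(1/34 + 1/35) = 0.048. Multiplied by the slope (0.39, 0.56, 0.74), a one-SE chance imbalance moves the unadjusted incremental QALY by 0.019, 0.027 or 0.036. This is not a further effect: at r = 0.5, 0.0274² + 0.0271² = 0.0385².

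**Less favourable cases.**
- Equal correlation 0.1: R² = 0.2125² / 0.3531 = 0.128, reduction 6.6%.
- Baseline term left out of the QALY, equal correlation 0.3: R² = 0.2625² / 0.4156 = 0.166, reduction 9%.
- Baseline term left out, correlation 0.3 with baseline and 0.7 among follow-ups: R² = 0.2625² / 0.6156 = 0.112, reduction 5.8%.
- Baseline term left out, equal correlation 0.1: R² = 0.0875² / 0.3156 = 0.024, reduction 1.2%.

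**What the percentages do not depend on.** √(1 − R²) contains neither N nor the SD. The plan does not say whether 0.2 is the SD of the index or of its change. If it is the SD of change, the visit SD is 0.2 / √[2(1 − r)] = 0.17, 0.20 or 0.26. The SEs then fall from 0.029, 0.039 and 0.055 to 0.024, 0.027 and 0.030, with the same percentages. The plan's 14% dropout (29 versus 30 complete) raises both SEs and leaves the percentages as they are.

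**The case against.** The strongest reply is that the SAP is silent rather than wrong. It neither adopts nor excludes adjustment, and it expects a health economist to help develop the evaluation. An unadjusted difference is a valid estimator, and no observed imbalance is reported. This stands, and it is why the point is one of efficiency. The reference to a health economist still does not supply an estimator.

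Several stronger readings are tempting, and the documents do not support them.
- A reader might infer that the ICER would be biased or its bootstrap misleading. Randomization prevents systematic bias, and the bootstrap would show the larger uncertainty correctly.
- A reader might take 16% to 45%, or 9% as a floor, for the range of the gain. These figures only reflect the correlations chosen; the less favourable cases go lower, and correlations above 0.7 would give more.
- A reader might think that the shortfall to 69 patients enlarges the percentage gain. It hardly matters to the percentage; a small sample enlarges the absolute SE and the likely chance imbalance.
- A reader might expect the ICER interval to narrow by the same percentage. The documents contain no cost data, adjustment for baseline EQ-5D is not aimed at cost uncertainty, and that uncertainty may dominate.

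Two further objections hold and shape the fix. A model added after unblinding loses much of its value as pre-specification. And a regression on each patient's QALY needs a rule for missing visits, given ITT and the anticipated dropout.

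**Conclusion.** The point holds as a free improvement. The plan compares QALYs between arms without naming an adjustment for a baseline measure of the same quantity taken before randomization. An unadjusted comparison would be valid but less precise than it could be.

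Under the stated assumptions the SE of the incremental QALY falls by about 16%, 29% or 45% at equal correlations of 0.3, 0.5 or 0.7. The size in this trial cannot be determined from the documents and could be only a few percent if the correlation with baseline is low. The downside is small: even with no correlation to exploit, estimating the slope costs less than 1% of the SE. No consequence for the ICER interval or for the study's conclusion has been shown.

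**What to change.** Add to the Statistical analysis plan:

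1. Each patient's QALY is the area under the EQ-5D-3L index at 0, 3, 6 and 12 months. The incremental QALY is the arm coefficient from a regression of QALY on randomized arm and baseline index.
2. The regression is refitted in every bootstrap replicate, and the adjusted difference is used in the ICER and its uncertainty.
3. Patients with missing visits are handled by one stated method, consistent with ITT and identical in the adjusted and unadjusted analyses.
4. The unadjusted result is reported alongside.
5. The plan states whether this model was fixed before or after allocation was revealed for the companion trial. If after, it is labelled post hoc.

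The cost is a few sentences and one extra slope parameter, with no new EQ-5D data. The missing-visit rule takes the most thought, but a QALY analysis under ITT needs one with or without adjustment.

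### Does naming only the ICER with a bootstrap, and no willingness-to-pay range, leave the economic analysis unsound with 69 patients?

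*Combined protocol and SAP*

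**What the plan says.** The method is stated twice in the combined protocol and SAP. The Methods paragraph of the Brief Summary describes a cost-effectiveness analysis "presenting incremental cost-effectiveness ratio (ICER) and a non-parametric bootstrapping will be conducted to demonstrate the uncertainties surrounding the ICER". The Statistical analysis plan repeats that the result will be "presented as an incremental cost-effectiveness ratio (ICER) and a non-parametric bootstrapping will be conducted to demonstrate the uncertainties surrounding the ICER". Neither place says what form the bootstrap output will take. No willingness-to-pay value or range, net benefit, cost-effectiveness plane or acceptability curve appears anywhere in the document.

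Four other statements bear on the point:

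- **Problem statements.** There is a question on QALYs alone, and another on the cost differences between the processes "initiated by either a physiotherapist or a physician set against the differences in effects".
- **Outcome Measures.** The primary outcome is EQ5D-3L health-related quality of life. Six cost components are listed as secondary outcomes. The ICER is not itself an outcome measure.
- **Statistical analysis plan.** "The economic evaluation will be developed together with a health economist".
- **Expected results.** The stated hope is: "The results could clarify which profession that is most appropriate to be the primary assessor for patients with suspected knee osteoarthritis in primary care".

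**The concern.** An ICER divides the cost difference by the QALY difference, so its sign and size do not identify the quadrant. Cheaper-and-worse gives a positive ratio, as does costlier-and-better. A dominant option gives a negative ratio, as does a dominated one. If bootstrap replicates fall on both sides of a zero QALY difference and percentiles or a mean are taken on the ratio, opposite conclusions are pooled and the interval has no clear meaning.

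A second worry is the decision. Unless one arm is both cheaper and better, an ICER does not say which profession to prefer until it is compared with a threshold, and none is given.

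The timing adds to this. On allocation, the Randomization section says: "Group allocation was revealed when analyzing data for the other clinical trial". That other trial supplied the EQ5D data, while under Patient recruitment "data collection regarding cost variables has not started yet". The QALY side could therefore be known by arm before costs are, and a threshold picked later could be picked to suit the result. Enrolment of 69 against a planned 100 makes a QALY difference near zero look more likely.

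**Working it through.** **1. The plan's own figure.** The Sample size section gives a difference of 0.121, SD 0.2, two-sided 5%, 80% power and 14% dropout.

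n per group = 2 × (1.960 + 0.842)² × 0.2² / 0.121² = 42.9, rounded up to 43. Then 43 / 0.86 = 50. The stated 50 per group is reproduced.

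**2. Precision of the QALY difference.** EQ5D-3L was "collected at baseline (before randomization), 3-, 6- and 12 months follow ups". The area under the curve by trapezoids gives weights 0.125, 0.25, 0.375 and 0.25 (sum 1).

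Assumptions not in the document: SD 0.2 at every visit, common between-visit correlation r of 0.3 to 0.7, 69 patients split 35/34, and complete data. The plan does not say whether QALYs are adjusted for baseline, so both forms are shown.

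- Unadjusted SD = 0.2 × √(0.28125 + 0.71875r) = 0.141, 0.160, 0.177 for r = 0.3, 0.5, 0.7.
- Baseline-adjusted SD = 0.2 × √(0.265625(1 − r²) + 0.5(r − r²)) = 0.118, 0.114, 0.098.
- SE at 35/34 (multiply by √(1/35 + 1/34) = 0.241): 0.034-0.043 unadjusted; 0.024-0.028 adjusted.
- SE at 50/50 (multiply by √(1/50 + 1/50) = 0.2): 0.028-0.035 unadjusted; 0.020-0.024 adjusted.

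**3. How often replicates straddle zero.** Call a trial straddling if more than 5% of replicates lie on each side of zero. The 5% cut-off is a choice. With true QALY difference d, the probability is Φ(1.645 − d/SE) − Φ(−1.645 − d/SE).

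| True pattern | d (QALY) | 35/34 unadjusted; adjusted | 50/50 unadjusted; adjusted |
|---|---|---|---|
| Small difference (illustrative) | 0.02 | 84-86%; 78-82% | 82-85%; 73-78% |
| 0.121 at 12 months only | 0.121 × 0.25 = 0.030 | 77-82%; 64-72% | 71-78%; 54-64% |
| Linear growth to 0.121 | 0.121 × 0.5 = 0.0605 | 45-59%; 18-31% | 31-48%; 8-18% |
| 0.121 from month 3 | 0.121 × 0.875 = 0.106 | 7-20%; under 2% | 2-9%; under 1% |

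Straddling is thus likely for a small or late effect at either sample size, and uncommon if the planned effect is early and sustained. Fewer patients matter most for a gradual effect. If 14% of the 69 are lost (30/29), the 12-month-only row becomes 79-83%; 68-74%.

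**4. Does straddling damage the planned analysis?** Only if the ratio itself is summarised across replicates. The plan says bootstrapping will show the uncertainty around the ICER. It does not commit to percentiles of the ratio or to a mean of ratios. Plotting the paired cost and QALY differences satisfies the same sentence and keeps the quadrants apart.

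**5. Would net benefit settle the matter?** Net benefit at willingness-to-pay λ is λ × (QALY difference) − (cost difference). At high λ the QALY term dominates, so its 95% interval includes zero about as often as the QALY interval does. For the 12-month-only effect at 35/34, replacing 1.645 by 1.96 in the formula gives 86-89% unadjusted and 75-81% adjusted. The interval would be interpretable, but no narrower in what it can tell the reader.

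**The case for a change.** The strongest case for a change is that leaving the evaluation to be developed with a health economist defers the choices and does not prespecify them. A cost-effectiveness plane cures the pooling of quadrants but still supplies no threshold, and the threshold matters even when no replicate crosses zero. Patients in both arms may see the other profession after the first assessment, which could dilute the contrast and make a small effect plausible. Since allocation and EQ5D data were available before costs, the moment to fix the range is before costs are compared by arm. Doing so costs only a few lines.

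Much of this stands. The range is absent, deferral is not prespecification, and a range written down early would be worth having. It does not show that the analysis as planned would mislead. No threshold or decision rule is planned, so there is none to bend, and the sentence about the most appropriate profession is an aspiration. The cost and QALY differences are both to be compared, so the quadrant of the point estimate is visible and a reader can put any λ into the net-benefit formula. An acceptability curve over a broad range, if the health economist adds one, leaves little to select. Naming a single reference value and moving the conclusion from the ICER to net benefit would go beyond what the gap calls for.

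**Conclusion.** No change to the plan is required. The ICER with a non-parametric bootstrap is a valid approach. What is missing is the form of the output and a willingness-to-pay range, which analysts working with a health economist can be expected to fill sensibly, for example with a plane, quadrant shares and an acceptability curve from the same replicates. That is good reporting, not a correction of method.

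The numerical part of the worry is true only on its own condition. With 69 patients, straddling occurs in roughly 64-86% of trials for a small or late effect, and in at most 20% if 0.121 is reached by month 3 and held. For the small or late cases the planned 50 per group would still give roughly 54-85%, so the shortfall in enrolment is a minor contributor there. It counts for more with linear growth: 45-59% against 31-48% unadjusted.

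These figures rest on an assumed correlation of 0.3 to 0.7, a near-equal split, complete data and SD 0.2 at each visit. The Sample size section attaches that SD to an improvement, so it may be the SD of change, which could move the figures either way. The conclusion does not depend on them, because the harm requires a summary of the ratio that the plan does not commit to.
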